#### **8.6.5 Baseline (Day 1)**

Subjects will return to the clinic for the Baseline visit at which compliance with eDiary completion and hot flush data will be reviewed. Subjects who comply with all other selection criteria, who have completed the diary for at least 9 days, and who have recorded an average of at least 7 moderate or severe hot flushes per day (including night-time) over the last 7 days that the eDiary was completed may enter the 12-week double-blind portion of the study and be randomised to one of 40 mg, 80 mg, 120 mg or 160 mg NT-814 or placebo treatments. The mean number of hot flushes will be calculated programmatically by the eDiary vendor and the outcome made available to the site.

Subjects who **do not** record an average of at least 7 moderate or severe hot flushes per day (including night-time) over the last 7 days that the eDiary was completed, or who are not compliant with eDiary completion will be deemed Screen Failures and will not be able to continue into the study. Limited data will be collected for subjects who withdraw from the study after providing informed consent but prior to randomisation onto the study (Screen Failures).

The Baseline visit will be Day 1. Prior to dosing on Day 1, the following assessments will be completed:

- Review of inclusion/exclusion criteria, including eDiary data
- Symptom directed physical examination
- Vital signs (after resting for  $\geq 5$  mins, see Section 10.3.8)
- 12-lead ECG
- Blood samples for clinical chemistry, haematology and plasma bone turnover markers
- Urine sample for urinalysis

- 
- Subjects will be asked to complete the MenQoL-I, HFRDIS, Pittsburg Sleep Quality Index, Insomnia Severity Index, electronic Columbia Suicide Severity Rating Scale (eC-SSRS) and the Beck Depression Inventory II.
  - Review for adverse events and changes in concomitant medications

Eligible subjects will be randomised on Day 1 to NT-814 or placebo. Randomisation will be performed centrally via an interactive web response system (IWRS).

Subjects will be given their first dose of IMP in the clinic and take all subsequent doses at home once a day in the evening (starting the following day) for a total of 12 weeks. At the baseline visit, subjects will be provided with IMP sufficient for the next 4 weeks.

Subjects will continue to complete the eDiary twice a day throughout the study until the Final Follow-up visit at Week 16.

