#### 4.2.12. Visit Windows

Visit windows are defined in Table 2, and are applicable for efficacy (except diary data) and safety.

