#### 4.3.2. Efficacy analysis

At each interim review, summaries by dose group will be provided on the FAS for each of the following:

- Mean daily frequency of moderate and severe HF at baseline, mean daily frequency of moderate and severe HF at each study week, including Week 4 and mean change and percent change from baseline in the mean daily frequency of moderate and severe HF at each study week.
- Mean severity of moderate and severe HF at baseline, mean severity of moderate and severe HF at each study week, including Week 4, and mean change from baseline in the severity of moderate and severe HF at each study week.

If available, summaries of the same data at later time-points (Week 8 and Week 12) will also be reviewed.

Mean daily frequency at each study visit will be calculated using the same method as the one described in section 4.2.11 based on the last 7 days with at least one available data in the evening and/or morning before the corresponding visit.

Mean weekly severity at each study visit will be calculated using the following:

$$\frac{[(\text{number of mild hot flushes for 7 days}) \times 1 + (\text{number of moderate hot flushes for 7 days}) \times 2 + (\text{number of severe hot flushes for 7 days}) \times 3]}{\text{total number of mild, moderate and severe hot flushes over 7 days}}$$

If the number of hot flushes is equal to 0, then the mean severity will be set to 0.

These 7 last days with available data should be within the 14 days prior to the CRF study visit, so in the following window: [CRF Visit date – 14; CRF Visit date], with at least one day within

the last 7 days prior to the study visit. In case of withdrawal, the day this ET visit happened will be checked to see in which windows it is and then to assign the corresponding timepoint. If a CRF visit has already been done at that timepoint, then the CRF visit date will be used. If less than 7 days fulfil these rules, only the correct data will be used in the derivation, and formula will be adjusted using the right number of days as denominator. Morning diary data on the day of a Visit will be included in the derivation as the morning diary is actually associated with the previous calendar day (a complete day is an evening then a morning diary).

In addition, emerging data will be evaluated via the two adaptive following algorithms to evaluate the emerging data at Week 4:

- (i) a Bayesian adaptive Emax (S-shaped) dose-response model fit, and

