#### 4.6.1. Co-primary analysis

The co-primary endpoints are the change from baseline in the mean daily frequency and mean weekly severity of moderate and severe hot flushes at Weeks 4 and 12.

For each timepoint (Baseline, Week 1, Week 2, Week 4, Week 8, Week 12) summaries will be produced which use data from the 7 days with at least one available eDiary data entry in the evening and/or the morning before the Visit date:

- These 7 days do not need to be consecutive.
- As the data entered in the morning diary is assigned to the previous calendar day (a diary day comprises an evening and a morning entry, in that order) the morning diary with the same calendar date as the Visit day may be included in the calculation.
- For Week 1, the first 7 post-baseline days with at least one available data in the evening and/or the morning will be used.

The methods for calculating the endpoint are the same as described in section 4.2.11.

Absolute and changes from baseline in the mean daily frequencies and mean weekly severity of moderate and severe hot flushes will be summarised by treatment group. Percent changes from baseline in the mean daily frequencies will be also summarised.

The change from baseline will be calculated as follow:

Mean daily frequency (or mean severity) at week 4 (or Week 12) – Mean daily frequency (or mean severity) at baseline.

The percent change from baseline will be calculated as follow:

(Change from baseline / Mean daily frequency at baseline) \* 100.

The mean change from baseline and the corresponding 95% confidence interval (CI) will be displayed graphically by visit on the observed values and by treatment groups.

Bar graphs of the change from baseline at Week 4 and Week 12 will be produced for each treatment group.

The change from baseline endpoint will be analysed using a Mixed-Effect Model Repeated Measures (MMRM) incorporating post-randomization data collected up to treatment discontinuation at weeks 12 (Week 1, 2, 4, 8 and 12 will be included; Week 16 visit data will not be included in the model) and with consideration of the variance-covariance matrix of the repeated measures.

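### Diary values exist only relative to an attended visit: a missed Week 4 or Week 12 visit leaves complete eDiary days unused, and the 14-day look-back has no floor at first dose

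*SAP*

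**What the plan says.** Protocol 8.6.5 makes diary completion independent of attendance: "Subjects will continue to complete the eDiary twice a day throughout the study until the Final Follow-up visit at Week 16". Protocol 11.9.1 defines the co-primaries on the 7 days before the Week 4 and Week 12 visits.

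SAP 4.3.2 computes each value "based on the last 7 days with at least one available data in the evening and/or morning before the corresponding visit". It then sets the limits: "These 7 last days with available data should be within the 14 days prior to the CRF study visit". One or more of the days used must come from the week leading up to the visit. With fewer days, "If less than 7 days fulfil these rules, only the correct data will be used in the derivation", and the denominator is adjusted. SAP 3.2 refers to these rules for the days used in the analysis of frequency and severity, so they reach the final analysis. SAP 4.6.1 also counts back from the visit date.

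Three provisions might have supplied an alternative anchor:

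- The Table 2 windows are "applicable for efficacy (except diary data) and safety", so they assign no diary days to a week.
- Early termination has its own rule: "In case of withdrawal, the day this ET visit happened will be checked to see in which windows it is". It applies only on withdrawal.
- The blinded data review in SAP 4.2.12 handles visits held outside their window, not visits that were not held.

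SAP 4.2.7 generally makes no substitution for missing data. A restriction to post-baseline days is stated for one week only: "For Week 1, the first 7 post-baseline days with at least one available data in the evening and/or the morning will be used".

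**The concern.** **Missed visit.** Without a visit date there is no window, so a subject with a full diary gets no value for that week. At Week 4 or Week 12 this removes two co-primary values that were observed, and leaves them to the MMRM's missing-at-random assumption. Per-protocol status is also left open: diary compliance at those weeks (PD 3.10 and 3.11 in SAP 3.2) is calculated on the same 7 days, which are undefined without an anchor.

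**No floor at first dose.** The run-in diary is the same eDiary, started at Screening Visit 2. For an early Week 2 visit the 14-day look-back extends into it. A post-baseline value could therefore contain placebo run-in days that also form the baseline. Week 2 is one of the visits in the primary MMRM, which has an unstructured covariance matrix.

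**Working it through.** **Reproducing the plan's figures.** Target day plus or minus the allowed window gives 15 ± 3 = Day 12-18, 29 ± 3 = Day 26-32, 57 ± 4 = Day 53-61 and 85 ± 4 = Day 81-89. All match the protocol-specified intervals in SAP Table 2. There is no Day 0 (SAP 4.2.8). The visit-day morning entry belongs to the previous diary day (SAP 4.3.2), so the usable diary days run from visit - 14 to visit - 1.

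**Missed visit.** Suppose all other visits are on target and the diary is complete.

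- Week 4 missed: Week 2 (Day 15) uses Days 8-14 and Week 8 (Day 57) uses Days 50-56. Days 22-28 feed no value.
- Week 12 missed: Days 78-84 feed no Week 12 value.
- Contrast: if the windows in the early-termination rule are those of Table 2, a subject who withdraws with a visit on Day 72 falls in the Week 12 interval (Day 72-99). Days 65-71 can then supply a Week 12 value, while the subject who stayed gets none.

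For scale only, take 30 completers per arm, a difference of 4 and SD 4.4 (SAP 4.1), use the normal approximation, and let the MMRM recover nothing. Pairwise power is 94.1% with no loss. With 3%, 5% or 10% of values lost in each arm it is 93.4%, 92.9% or 91.6%. These loss rates are assumptions. Losing 1 or 2 of 30 per arm multiplies the standard error by √(30/29) = 1.017 or √(30/28) = 1.035.

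**No floor at first dose.** Run-in days enter only if 6 or fewer post-dose days in the window have an entry. Let n be the post-dose diary days in the window and m an assumed probability that both entries of a day are missing, independent between days. Then P = Pr[Binomial(n, m) ≥ n - 6].

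| Week 2 visit | Look-back starts | Run-in days in window | n | Blank days needed | P at m = 5% / 10% / 20% / 30% |
|---|---|---|---|---|---|
| Day 12 | Day -3 | 3 | 11 | 5 | 0.01 / 0.3 / 5.0 / 21% |
| Day 13 | Day -2 | 2 | 12 | 6 | 0.001 / 0.05 / 1.9 / 11.8% |
| Day 14 | Day -1 | 1 | 13 | 7 | about 0 / 0.01 / 0.7 / 6.2% |
| Day 15-18 | Day 1 or later | 0 | 14 | none | 0 |

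These probabilities apply only to subjects who attend early.

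If k of the 7 days are run-in days at the baseline level and the true reduction is R per day, the Week 2 change is understated by kR/7. At the SAP's lower target, R = 6, this is 0.86 (k = 1) to 2.57 (k = 3) per day for that subject. At R = 8 it is 1.14 to 3.43. With a Day 12 visit, k = 3 of 7 requires 7 of the 11 post-dose days to be blank.

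**Reach to the co-primaries.** The earliest in-window Week 4 and Week 12 visits, Days 26 and 81, look back to Days 12 and 67. Run-in days cannot enter those values.

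**The case against.** The strongest reply is that visit anchoring is the protocol's own definition, and that the SAP's 14-day look-back recovers data rather than discarding it. That stands. The gap is the missing rule for a visit not held, and filling it extends the protocol definition and must be recorded as such.

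The missed-visit loss is also inferred from silence, and it is narrow. The subject must stay in, keep the diary and never attend, even late. Protocol 9.2 and 9.4 supply 4 weeks of drug plus 4 days' overage, with dispensing at Weeks 4 and 8, so a subject continuing treatment has to come in around Week 4. Nothing comparable applies at Week 12. One missing visit among observed ones is a mild use of missing at random. These arguments limit the size of the point but do not supply a rule.

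On the look-back, the MMRM paragraph in SAP 4.6.1 speaks of data after randomisation, which signals intent, but the derivation rule does not apply it. The full analysis set's requirement of 7 post-treatment days should exclude very early terminators. It does not prevent a sparse early fortnight in a subject who continues.

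Two stronger readings are tempting:

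- A reader might infer that an early Week 2 visit by itself contaminates the value. It does not: with a complete diary no run-in day enters.
- A reader might infer that Week 1, which has no stated end day, also needs correcting because it can share days with Week 2. The documents do not show harm. A complete diary with a Day 12 visit already shares Days 5-7 (Week 1 uses Days 1-7, Week 2 uses Days 5-11). The unstructured covariance accommodates correlation between the two values, and limiting Week 1 to Days 1-7 would leave that overlap while discarding days in sparse reporters.

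**Conclusion.** The point holds in two limited parts.

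First, there is no rule for a subject who keeps the diary but misses a visit, so observed co-primary data can go unused. This matters more because the data are already collected and no imputation is needed to recover them. It should be uncommon, and more likely at Week 12 than at Week 4. Its size cannot be stated from the documents; under the assumed 3-10% loss, pairwise power falls by 0.7 to 2.5 percentage points at most.

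Second, the missing floor at first dose is a genuine gap in a stated window, but a rare one. It needs both a Day 12-14 visit and at least 5 to 7 fully blank post-dose days. It affects Week 2 directly, and Weeks 4 and 12 only through the MMRM.

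Neither part shows that the primary comparison is biased. Both are worth closing before database lock so that they are not settled in programming afterwards.

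**What to change.** Add two rules to SAP 4.3.2 and 4.6.1, applied at the interims and the final analysis:

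- **(a)** Where no visit took place for a week, anchor the window to the target day (Day 15, 29, 57, 85 or 113) and use the diary days available. For the MMRM, use only days up to treatment discontinuation, because protocol 7.4 lets a subject stop drug and remain in follow-up. With a complete diary on treatment this recovers 7 of 7 days: Days 22-28 for Week 4 and Days 78-84 for Week 12.
- **(b)** Only diary days from the first randomised dose onward may enter any post-baseline value. A Day 12 visit then has 11 eligible days and no run-in days.

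Record (a) in SAP section 5, which now reports no changes, as an extension of the protocol's visit-anchored definition. Leave the Week 1 rule as it is.

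The cost is minor programming and a small documented departure from the protocol wording. Where the visit was held and the diary is complete, no in-window value changes.

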inhibitors of CYP3A4	boceprevir, cobicistat, danoprevir and ritonavir, elvitegravir and ritonavir, grapefruit juice, indinavir and ritonavir, itraconazole, ketoconazole, lopinavir and ritonavir, paritaprevir and ritonavir and (ombitasvir and/or dasabuvir), posaconazole, ritonavir, saquinavir and ritonavir, telaprevir, tipranavir and ritonavir, troleandomycin, voriconazole  aprepitant, cimetidine, ciprofloxacin, clotrimazole, crizotinib, cyclosporine, dronedarone, fluconazole, fluvoxamine, imatinib, tofisopam, verapamil, troleandomycin, ciprofloxacin
P-glycoprotein inhibitors	azithromycin, conivaptan, cyclosporine, diltiazem, erythromycin, felodipine, ketoconazole, quinidine, ranolazine,  amiodarone, carvedilol, clarithromycin, dronedarone, itraconazole, lapatinib, propafenone, quinidine,
P-glycoprotein substrates with a narrow therapeutic range	Digoxin
Prohibited from Screening Visit 2 until Week 12	
Strong or moderate inducers of CYP3A4	rifampicin, carbamazepine, efavirenz, bosentan, modafinil, St. John's Wort, enzalutamide, mitotane, phenytoin, etravirine

[figure not shown]
**APPENDIX B: PHASE 2B ADAPTIVE DOSE-FINDING DESIGN FOR NT-814  
EFFECT ON REDUCTION OF HOT FLUSHES**[name]  
18 July 2018**INTRODUCTION AND PURPOSE**

A Phase 2b dose-finding placebo-controlled trial of NT-814 treatment with four different doses for 12 weeks aimed at reduction of hot flushes is being planned. Adaptive design options are being considered to modify randomization ratios to the NT-814 doses based on accumulating data. This report summarizes several example adaptive design options along with their performance characteristics for an initial assumed example set of potential TRUE underlying dose-response curves. The primary endpoints for the trial are hot flush frequency and severity; however, the adaptive design simulation software cannot handle multiple endpoints. Hence, the scenarios evaluated focus on reduction of hot flush frequency.

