The two adaptive algorithms are (i) a Bayesian adaptive Emax (S-shaped) dose-response model fit at each IA (COMPASS User Manual), and (ii) a model based on classical T-statistics at each IA (Ivanova, 2008). The Emax design uses a "vague" Bayesian prior distribution on each of the four parameters of the S-shaped Emax model in combination with the observed data to estimate the posterior distribution of the Emax model parameters from which estimates of mean response at each dose are obtained, along with their SE's. Then randomization ratios are chosen for the next cohort to minimize the variances of the resulting Emax model estimates at two target levels of response, namely hot flush reductions of 6 per day and of 8 per day. The Emax algorithm was set up to recommend stopping randomization to a given dose if (a) the probability is > 90% that the mean hot flush reduction is at least 8 at that dose, or (b) the probability is <20% that the mean hot flush reduction is at least 5 (i.e., >80% probability that the mean hot flush reduction is <5).

The T-statistic design relies on isotonic regression (i.e., best-fit non-decreasing dose-response curve) derived estimated means for each dose and then computes the resultant T-statistic for estimated mean difference from each target level of response (hot flush reduction of 6 and of 8) for each dose. Then the subjects in the next cohort are split among the two doses with T-statistics pointing closest to each target level of response and placebo. The sample sizes of each cohort are always 10 on placebo for the 2 IA design, and always 5 on placebo for the 5 IA design, to yield N=30 on placebo for the final analysis. For the simulations, the subjects assigned to the active doses are randomized according to the randomization ratio indicated by the adaptive design algorithm for each cohort after the first. The only stopping criteria recommendation available for the T-statistic in the simulation software (Cytel's COMPASS V1.1) is futility stopping; hence, if probability of a significant difference from placebo is <5% for a given dose based on the IA results, then the algorithm recommends that dose is dropped from any further randomization to it.

The 24 scenarios (4 DR curves X 3 cohort sizes X 2 design algorithms) were each simulated 500 times, and the following performance characteristics, averaged across the 500 simulations, were summarized in Tables 1a and 1b

- Average total sample size

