.. Subjects will be analysed according to randomised treatment. This is the sensitivity efficacy analysis set for the study planned only if more than 20% of subjects are excluded from the FAS.

**Per Protocol (PP) Set:** All subjects in the FAS who completed the 12 week treatment period excluding those identified as having relevant protocol deviations (see Section 3.2). The list of relevant protocol deviations leading to exclusion from the PP population has been finalized during the blinded data review prior to database lock and unblinding of treatment allocation. Subjects will be analysed according to randomised treatment. This is the secondary efficacy analysis set for the study.

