### 4.3. Interim Analyses

The first IA will be conducted after efficacy data from frequency and severity of HF is collected through Week 4 from 30 patients randomized in equal proportions to the four NT-814 doses and placebo.

Based on DRC review of the IA results, randomization ratios for subsequent enrolled patients may be changed to optimize the allocation of subjects to doses with target levels of weekly average daily HF frequency reduction from baseline of 6 and 8; and HF severity reduction from baseline of 0.66 and 0.88 (Study RELENT-1). Adaptive design algorithm will be based on Bayesian Emax dose-response modelling [1] and / or T-statistic adaptive dose-finding design [2]. The DRC will have dose assignment recommendations by each of those adaptive dose-finding algorithms and assign the randomization ratio that best integrates the objectives of the trial and the adaptive design results. Randomisation ratio recommendations will also take into consideration emerging safety findings as well as the need to allocate sufficient subjects to a dose of interest to enable an adequate assessment of safety to be made.

Subsequent IA's will be conducted similarly, after Week 4 data from each cohort of ~30 additional patients become available.

The DRC will evaluate stopping criteria per the IA algorithms as described in Appendix B of the protocol and decide on stopping assignment of subjects to specific doses or stopping the trial for an efficacy conclusion and dose choice for subsequent study or futility.

The review of efficacy will be based only on the frequency and severity of HF recorded by subjects in the electronic diary (eDiary).

The review of safety will be based on adverse event and early withdrawal information.

For each IA, a cut-off date will be applied such that data will be included until the date the last patient in the analysed cohort completes the Week 4 visit.

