- (ii) a model based on isotonic regression (T-stat)

The models have been developed using the following prior assumptions:

1) On frequency of hot flushes:

- The mean reduction in the mean daily number of moderate and severe HF's in the placebo group is 4 per day
- Two target levels of test treatment: mean reduction from baseline in the mean daily number of moderate and severe HF's of 6 and 8
- Common standard deviation (SD) of 4.4
- Stopping guidelines for Emax if (a) the probability is > 90% that the mean hot flush reduction is at least 8 at that dose, or (b) the probability is <20% that the mean hot flush reduction is at least 5 (i.e., >80% probability that the mean hot flush reduction is <5).

2) On severity of hot flushes:

- The mean reduction in the severity of moderate and severe HF's in the placebo group is 0.44 per day
- Two target levels of test treatment: mean reduction from baseline in the severity of moderate and severe HF's of 0.66 and 0.88
- Common standard deviation (SD) of 0.55
- Stopping guidelines for Emax if (a) the probability is > 90% that the mean severity hot flush reduction is at least 0.88 at that dose, or (b) the probability is <20% that the mean severity hot flush reduction is at least 0.22 (i.e., >80% probability that the mean hot flush reduction is <0.22).

Emerging data (mean change from baseline in the frequency/severity of moderate and severe HF at Week 4) will be entered in COMPASS software using the Execute module. The following steps will be followed:

- Raw data from eDiaries will be provided to the Cytel blinded team by ERT, the CRF data will be provided by the Pharm Olam Data Management team
- Efficacy endpoints to be presented (see above) will be generated by the Cytel blinded team using the derivation described in this SAP
- Statistical descriptive tables for these endpoints will be produced by the Cytel blinded team using a dummy randomisation list

- Programs will be rerun by the Cytel unblinded team using the real randomisation list provided to the Cytel unblinded statistician
- Endpoint data for each patient along with their treatment arm will be entered into COMPASS.

Prior distributions, defined above and used for the simulation, will also be entered in the software. COMPASS has been developed as a software package for design of adaptive early stage trials within Cytel's suite of software programs for design, analysis, and implementation of clinical trials.

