Outputs from the software after having the randomisation code applied will be provided to the DRC members. The outputs comprise:

- Summary tables showing: subject allocation, observed and model-estimated mean results, by dose and pooled SD's, posterior probability (for Emax) or conditional power (for T-stat) and summary statistics
- New subject data with a new recommended randomisation ratio, considered the most efficient per the method.

A summary of the results provided by COMPASS included the allocation probability (related to the next randomisation ratio) recommended from the Emax and T-stat analyses, based on the frequency and severity of HF, will be provided by the unblinded statistician to the DRC members in a separate report. The DRC will take into consideration these results in recommending the randomisation ratio for the next cohort of subjects.

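### The interim Emax futility cut for hot flush severity (0.22) is half the assumed placebo reduction (0.44), so it almost never flags a placebo-like dose

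*SAP*

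**What the plan says.** SAP section 4.3.2 lists the assumptions behind the two interim algorithms, first for frequency and then for severity.

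- Frequency: placebo reduction 4 per day, targets 6 and 8, SD 4.4. The Emax futility limb is "b) the probability is <20% that the mean hot flush reduction is at least 5".
- Severity: "The mean reduction in the severity of moderate and severe HF's in the placebo group is 0.44 per day", targets 0.66 and 0.88, SD 0.55. The Emax futility limb is "b) the probability is <20% that the mean severity hot flush reduction is at least 0.22", and the same sentence restates it as a probability above 80% of a reduction below 0.22.

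SAP section 4.3 adds: "The DRC will evaluate stopping criteria per the IA algorithms as described in Appendix B of the protocol". Appendix B gives the Emax cuts for frequency only and says of its simulations that "the scenarios evaluated focus on reduction of hot flush frequency". It also describes a T-statistic futility rule, under which a dose is dropped "if probability of a significant difference from placebo is <5% for a given dose based on the IA results". All of this is advisory. SAP section 4.3.2 ends: "The DRC will take into consideration these results in recommending the randomisation ratio for the next cohort of subjects".

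**The concern.** A futility cut is meant to pick out doses unlikely to be worth continuing. For frequency it does so: 5 is above the assumed placebo response and below the lower target. For severity the cut is below the assumed placebo response, so a dose that behaves exactly like placebo sits comfortably on the continue side.

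The efficacy limb of the same guideline uses 0.88 as an absolute reduction, and the targets are stated as reductions from baseline. The natural reading of 0.22 is therefore also absolute. The value appears twice, so a text-extraction error is unlikely.

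Severity accounts for two of the four co-primary endpoints, and the severity outputs go to the DRC beside the frequency outputs when it recommends allocation. Absence of a severity flag could be read as support for keeping a dose when it says almost nothing about whether the dose beats placebo.

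**Working it through.** **Check on the plan's own figure.** The documents state no flagging probability for either cut. The nearest figure that can be reproduced is the sample size in SAP section 4.1: 33 per group for 95% power, difference 8 − 4 = 4, SD 4.4, two-sided 0.05. The noncentral t gives 94.7% power at 32 per group and 95.3% at 33, so 33 is reproduced.

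**Position of the cuts.**

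| Level | Frequency | Severity | Ratio severity/frequency |
|---|---|---|---|
| Placebo | 4 | 0.44 | 0.11 |
| Lower target | 6 | 0.66 | 0.11 |
| Upper target | 8 | 0.88 | 0.11 |
| Futility cut | 5 | 0.22 | 0.044 |

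Relative to placebo the frequency cut is 5/4 = 1.25 and the severity cut is 0.22/0.44 = 0.50. On the 0.11 scale, 0.22 corresponds to 2 flushes per day, and 5 per day corresponds to 0.55. The value 0.22 also equals 0.66 − 0.44, the gap between the lower target and placebo, but the text does not call it a difference from placebo.

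**Probability of a flag.** Take a flat prior, known SD and each dose on its own. The posterior probability of reaching the cut is below 20% when the observed mean reduction is less than cut − 0.8416 × SE, with SE = SD/√n. Hence

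P(flag) = Φ((cut − true mean)/SE − 0.8416).

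The first interim has 30 subjects in five equal groups, so n = 6 per dose. Each further cohort of about 30 adds 6 under equal allocation.

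Worked case, severity at n = 6 with a true mean of 0.44: SE = 0.55/√6 = 0.2245; (0.22 − 0.44)/0.2245 = −0.980; −0.980 − 0.842 = −1.822; Φ = 0.034. The observed mean would have to be below 0.22 − 0.8416 × 0.2245 = 0.031.

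For a dose truly equal to placebo:

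| n per dose | Severity, cut 0.22 | Observed severity reduction needed to flag | Frequency, cut 5 | Observed frequency reduction needed to flag |
|---|---|---|---|---|
| 6 | 3.4% | below 0.03 | 39% | below 3.49 |
| 12 | 1.3% | below 0.09 | 48% | below 3.93 |
| 18 | 0.6% | below 0.11 | 55% | below 4.13 |
| 24 | 0.3% | below 0.13 | 61% | below 4.24 |
| 30 | 0.1% | below 0.14 | 66% | below 4.32 |

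Over all five looks (400,000 simulated sequences of cumulative means) the chance of at least one flag is 4.3% for severity and 79% for frequency. Over four looks it is 4.3% and 74%. A dose with a true severity reduction of 0.22, half the placebo response, is flagged 20% of the time at any n.

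**Sensitivity to the SD (assumed range).** With a severity SD of 0.40 to 0.80, the rate is 1.4% to 6.5% at n = 6 and 0.01% to 0.9% at n = 30.

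**Cross-check with borrowing across doses.** A grid-based four-parameter Emax fit with assumed vague priors was run on flat curves, with looks at 30, 60, 90 and 120 subjects. A given dose was ever flagged 0.2% to 0.7% of the time on severity and 90% to 97% on frequency. With looks at 50 and 100, this emulation stopped early on frequency in 77% of trials; Appendix B Table 2 gives 67.4% (3 cohorts) and 78.4% (6 cohorts). It is only an approximation to the planned software.

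**Two other readings, same flat-prior approximation, placebo-like dose, n = 6, 12 and 30.**

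- Cut of 0.55: 36%, 44% and 60%, and 75% over five looks. A dose truly at the lower target of 0.66 is flagged 9.2%, 6.3% and 2.6% of the time. The frequency rule at its lower target gives 8.1%, 5.2% and 1.9%.
- 0.22 as a difference from placebo, with SE = 0.55 × √(2/n): 44%, 55% and 76%.

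**The case against.** The strongest reply is that little depends on this flag. The limbs are labelled guidelines, and the DRC weighs them with the observed and modelled means by dose. Both algorithms are run on severity as well as frequency, so severity already has a placebo-relative futility check in the T-statistic rule. Reading that rule as current-trend conditional power below 5% with a final 30 per arm (an assumption, since no formula is given), it flags a placebo-like dose about 59% of the time at n = 6 and 67% at n = 12. A futility flag that rarely fires keeps a dose open and costs efficiency, not validity. This stands, and it limits the consequence.

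It is also fair that 0.55 is an inference. SAP section 4.3 attributes the severity targets to RELENT-1, no text says that severity was scaled from frequency, and the SD does not follow the 0.11 ratio (0.55/4.4 = 0.125). A deliberately lenient severity rule is possible, and the DRC Charter, which is not among the documents, may explain it. The percentages are approximate, and reviews after the first are optional, so five looks is the full planned sequence, not a certainty.

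None of this explains a cut below the assumed placebo response. Borrowing across doses changes the decimals but makes the severity flag rarer still.

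**Conclusion.** The point holds. This is an inconsistency between stated design parameters, not a slip in a calculation. As written, the severity futility limb flags a placebo-like dose about 3% of the time at the first interim and about 4% over five looks, and at each successive look the rate falls. The matching frequency limb rises from 39% to 66%. These rates rest on a flat prior, known SD, equal allocation and each dose taken separately; the direction does not depend on them.

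The scope is one limb of one algorithm on one endpoint. Other rules and the DRC can still remove an ineffective dose, and the final MMRM comparisons do not use the cut. It should be fixed, but it does not threaten the trial's main conclusions.

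**What to change.** Reconcile the severity cut with the 0.44 placebo assumption, or state why 0.22 was chosen. Two readings would remove the conflict and are given as illustrations only. The cut could follow the scaling of the other severity levels, which gives 0.11 × 5 = 0.55. Or 0.22 could be a difference from placebo, in which case the SAP should say so and it should be entered that way. Whichever is adopted, report the severity rule's operating characteristics, since Appendix B has none.

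Before an interim, this costs one number or phrase in the SAP and the software set-up, plus a short simulation. That stage has probably passed: SAP section 3.1 says the list of deviations for per-protocol exclusion "has been finalized during the blinded data review". If interims have run, document the cut actually entered in COMPASS, re-run the severity flags on the stored interim data with the reconciled cut, and report any difference in the CSR. No new data are needed.
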